9.2 Exclusion Criteria

Participants meeting any of the following exclusion criteria are not eligible to enrol in this trial.

- 1. Patients with cancers of the transverse and left colon (due to difficulty in defining D3 lymphadenectomy in these anatomical locations)
- 2. Past history of hypersensitivity reactions to 5-ALA or colorimetric dye.
- 3. Acute or chronic porphyria or a family history
- 4. Patients with synchronous colonic or rectal cancer (but not benign polyps)
- 5. Patients with co-existent inflammatory bowel disease, such as Crohn's disease, ulcerative colitis or active diverticulitis, which may influence the lymphatic uptake of 5-ALA
- 6. Pregnant (positive pregnancy test) or breast feeding. 5-ALA has unknown teratogenic and abortifacient effects.

In women of childbearing potential (defined as any female who has experienced menarche and who is not postmenopausal or permanently

sterilised e.g. tubal occlusion, hysterectomy, bilateral salpingectomy). a pregnancy test will be performed and evidence of a negative result will be required prior to entry into the study. In females of child bearing potential, or those patients with partners of child bearing potential trial investigators will advise on appropriate contraception (e.g. barrier method) from the point of registration to 30 days postop.

- 7. Received an investigational medicinal product at any dose within 28 days before registration
- 8. Poorly controlled or serious medical or psychiatric illness that, in the Investigator's opinion, is likely to interfere with participation and/or compliance in this clinical trial.

Where possible, the study population will be enriched with locally advanced colon cancers (CT findings of a T4 tumour, T3 tumours with an extramural depth of >5mm, as per FOxTROT definition) to obtain as much information as possible on 5-ALA for lymph node metastases.

Concerns regarding a patient's eligibility can be discussed with the SJUH Research Fellow or Chief Investigator.

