Appendix 2: Radiology proforma

All patients will have baseline staging CT of the thorax, abdomen and pelvis as part of standard care at a maximum of 8 weeks prior to surgery. Abdominal imaging will be performed in the portal venous phase at 65 seconds. Reconstructed slice thickness 5mm axial & 3mm coronal planes for the abdomen.

All primary tumours will be given a proposed radiological TNM staging (according to TNM 5 due to its reproducibility) and include assessment for extramural vascular invasion (V).

Tumour location will be indicated according to the following locations:

□ *Caecum* (segment proximal to or involving ileocaecal valve)

□ *Ascending colon* (segment distal to ileocaecal valve and proximal to the initial angulation of the hepatic flexure)

□ *Hepatic Flexure* (segment distal to the initial angulation of the hepatic flexure to the proximal border of the falciform ligament)

□ *Sigmoid colon* (segment distal to the level of the left iliac crest to 15 cm proximal to the anal verge)

Tumour morphology

Polypoidal Flat Semi annular Annular

Tumour length (mm): _____

T stage

T2 or less (limited by muscularis propria)

□T3 not breaching serosa

T4a penetration of serosa with extension into adjacent organs

T4b penetration of serosa and peritoneal surface with perforation of bowel

N stage

Number of visible nodes______

Number of malignant nodes

□**N0** - none

□N1 - 1-3 regional lymph nodes appear malignant

□N2 – 4 or more regional lymph nodes appear malignant

Size of largest malignant (mm) node_____

Node location: According to lymph node mapping – see Figure 1.

V stage

- □V1 Vascular invasion present or probably present
- □V0 Vascular invasion probably absent or absent

M stage

- □M0 no distant metastases
- □M1a distant metastases one organ
- □M1b peritoneal or distant metastases to more than one organ or distant nodes

Metastases location:

□Liver

□Lung

□Peritoneum

Other _____

Right colon vascular anatomy assessment

□lleocolic artery present

□Right colic artery present (arising directly from the SMA *not* ileocolic)

Diddle colic artery present

□Artery crosses anterior to SMV

□Artery crosses posterior to SMV

Mapping the lymph node stations

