Not opening the specimen through the tumour segment facilitates comparison of the cross sectional slices with MRI/CT imaging. The slices should be carefully inspected and the position of the tumour recorded according to the quadrants of involvement. The distance of direct spread outside the muscularis propria and the distance from the tumour to the nearest non-peritonealised margin should be recorded along with the tumour thickness. These measurements should be made initially from the slices and confirmed histologically e.g. by using the Vernier scale. Large blocks should be taken from the area closest to the circumferential margin wherever possible and also from any area where the tumour extends to within 3 mm of the non-peritonealised margin. Other blocks should be taken to allow at least 5 blocks of tumour to confirm presence or absence of extramural venous invasion. The number of any large blocks containing tumour can be subtracted from these 5. Likewise the peritoneal surface should be sampled by a minimum of 2 blocks if the tumour impinges on it (figure 3).

All of the local lymph nodes in the specimen should be identified, mapped, embedded and examined. The high tie (apical node) should be blocked separately to allow Dukes' staging to be conducted as should any lymph nodes marked (e.g. with a clip) by the surgeons to allow comparison with the intra-operative staging. The number of lymph nodes identified in each station (see below) should be noted on a diagram for subsequent mapping. If the nodes have not been marked by the surgeons, multiple nodes from the same station may be embedded in one block to cut down on the workload.

Figure 3: Suspected peritoneal/serosal involvement by tumour.

Histological reporting

We are using both Dukes' and TNM 5 for histopathological staging in this study, not TNM 6 or 7. This is because of the poor reproducibility of the TNM 6 definitions of extramural vascular invasion and lymph nodes. Thus we will be using the 3mm rule for nodal involvement, although these will be captured separately on the CRF. This allows the study to be consistent with other trials such as the Dutch TME trial and MRC CR07 trial. Dukes' staging allows easy communication between surgeons and the clinical team whereas TNM 5 gives more prognostic information, especially with respect to early tumours and local spread, e.g. peritoneal and direct spread (figure 3).

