The non-peritonealised resection margin is considered involved (i.e. an incomplete excision) if the tumour extends to within 1 mm of the inked margin. Measurement is best made by using a sheet of graph paper that is photocopied onto a sheet of acetate and cut to size. This can be provided if required and may be more easily used than the Vernier scale. This is shown in figure 4 and can also be used for measuring the EMVI to see if it is greater than 3 mm. No distinction is currently made between the various modes of non-peritonealised resection

margin involvement, e.g. direct spread, lymph node spread, vascular, etc. Although all are associated with an increased local recurrence rate, this may be lower in the case of involvement by tumour within a lymph node.

Figure 4: Rapid measurement of the distance from the tumour to the non-peritonealised resection margin by overlaying a simple grid.

Peritoneal involvement (pT4) should be diagnosed if tumour cells penetrate the peritoneal surface (figure 5).

Figure 5: Peritoneal involvement should be assessed by the method of Shepherd et al 1995 whereby tumour cells should be seen to penetrate through the serosa to lie on the surface of the specimen.

The grade of differentiation of the tumour should be defined by the predominant area of tumour and not on the area of the worst grade. Other types of differentiation, i.e. mucinous adenocarcinomas, signet ring and undifferentiated should be documented.

Grading the quality of surgery (mesocolic resection)

The quality of the mesocolic resection can be easily assessed using a combination of assessing the fresh specimen, fixed specimen and cross sectional slices. We recommend a three grade classification (table 1, figures 6/7), first used in the MRC CLASICC trial and subsequently used in NCRI FOxTROT. These systems have been demonstrated to be usable in the context of phase III clinical trials and have been shown to predict a higher risk of local recurrence in MRC CLASICC and overall survival in a large Leeds study. A second assessment of surgical planes will be made during the central review to identify inter-observer agreement. This will be done on the digital photographs.

Plane of	Short	Detailed description
dissection	description	
Mesocolic	Good quality	There should be an intact and smooth mesocolic
plane	specimen	surface with only minor irregularities. Any
		peritoneal or fascial defects must be no deeper
		than five millimetres. There should be smooth

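### The CT T-stage boxes in Appendix 2 have no place for a tumour that penetrates the serosa without organ extension or bowel perforation, although Appendix 3 calls peritoneal penetration alone pT4

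*Protocol*

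**What the plan says.** Section 11.1.1 requires CT scans to be reported for the trial on a dedicated proforma that includes the radiological T-stage. Appendix 2 is that proforma. Its staging system is stated as follows: "All primary tumours will be given a proposed radiological TNM staging (according to TNM 5 due to its reproducibility". The T-stage block then gives four options:

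- The lowest box is for tumours that stay within the muscle layer of the bowel wall.
- The next box, which has a single condition, reads "T3 not breaching serosa".
- The first of the two highest boxes joins two conditions: "T4a penetration of serosa with extension into adjacent organs".
- The second of them also joins two conditions, with a different second one: "T4b penetration of serosa and peritoneal surface with perforation of bowel".

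Appendix 3, the histopathology proforma, names the same system alongside Dukes' staging: "TNM 5 for histopathological staging in this study, not TNM 6 or 7". Its rule for serosal disease has one condition: "Peritoneal involvement (pT4) should be diagnosed if tumour cells penetrate the peritoneal surface".

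Three other places give the CT T-stage its role. Section 15.2 lists standardised preoperative CT reporting as a secondary endpoint, with the emphasis on lymph nodes. Section 8.1 says that the findings go straight into the protocol of the multicentre evaluation phase. The end of section 9.2 describes enrichment, where it can be achieved, with locally advanced tumours: "CT findings of a T4 tumour, T3 tumours with an extramural depth of >5mm".

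**The concern.** A staging item on a form should give every tumour exactly one answer. Here both T4 captions join serosal penetration to a further finding, while T3 excludes serosal penetration. That leaves a gap between T3 and T4, and the tumour in the gap is one that the protocol's own pathology rule treats as T4.

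What is at stake is the quality of the CT reporting standard. Two radiologists who see the same serosa-penetrating tumour could answer differently, and neither would be misreading the scan. A form with this gap cannot standardise the T item, and the gap would pass to more sites and readers in the evaluation phase. CT T4 is also one of the two enrichment criteria, so the label could be uncertain for some patients considered for enrichment.

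**Working it through.** No sample size, power or error rate is involved. The check is logical: apply the captions as written to each possible tumour and compare the result with the pathology rule.

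**Inputs.** The four captions come from Appendix 2, the pT4 rule from Appendix 3 and the enrichment criteria from section 9.2.

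**Setup.** Take tumours that extend beyond the muscularis propria, so that the lowest box is excluded. Describe each by three yes/no features: serosa penetrated (S), adjacent organ involved (O), bowel perforated (P). Serosa and peritoneal surface are treated as the same surface. Appendix 3 supports this: the caption to its Figure 5 describes peritoneal involvement as tumour cells passing through the serosa to reach the surface.

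**Conditions as written.** T3 needs S = no. T4a needs S = yes and O = yes. T4b needs S = yes and P = yes. In Appendix 3, pT4 needs S = yes only.

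| S | O | P | CT box (Appendix 2) | Appendix 3 peritoneal rule |
|---|---|---|---|---|
| no | no | no | T3 | not met |
| yes | yes | no | T4a | pT4 |
| yes | no | yes | T4b | pT4 |
| yes | yes | yes | T4a and T4b both fit | pT4 |
| yes | no | no | **none** | pT4 |

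Of the four combinations with the serosa penetrated, two resolve to one box, one fits both T4 boxes and one fits none. All four meet the Appendix 3 rule. The row without a box is the contradiction: both proformas name the same staging system, but only one of them can stage this tumour.

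**What a reader could do with that row.** There are three options, and the form does not choose between them:

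1. Leave the item blank, so that CT T-stage is missing.
2. Tick T3, which contradicts the T3 caption because the serosa is penetrated.
3. Tick T4b on the strength of its first half, ignoring the perforation condition.

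**Consequence for enrichment.** Under option 3 the tumour counts as CT T4. Under option 2 it still meets the section 9.2 description if its extramural depth exceeds 5 mm, and fails it on the label only if the depth is 5 mm or less. Under option 1 the form does not settle the matter. The direction is therefore not fixed.

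**Consequence for yield.** Section 8.1 plans on 10 node-positive patients out of 16 (10/16 = 62.5%). To move that figure one would need the share of recruits in the unboxed row, the share of those labelled T3 with a depth of 5 mm or less, and how often the label alone decides whether a patient is approached. The documents give none of these, so no change in yield is calculated.

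**The case against.** The strongest reply is that Appendix 2 makes TNM 5 the governing system, so the captions are shorthand and an experienced radiologist would stage such a tumour T4 anyway. That may be what happens in practice. It does not remove the contradiction, because the captions are the only criteria printed on the form, and the form exists to make readers agree.

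It can also be said that little depends on the item, and most of this stands. The progression rules in sections 8.1 and 17.1 use per-patient detection by 5-ALA against histology in node-positive patients, and CT T-stage plays no part in them. No stated endpoint compares CT T-stage with pathological T-stage, and the CT endpoint puts its emphasis on nodes.

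Three stronger readings are tempting, but the documents do not support them.

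- *Affected tumours are pushed into T3 and out of the enrichment group.* The T3 caption itself bars them, T4b is an equally available choice, and T3 tumours deeper than 5 mm are enriched as well. Enrichment is an aim and not an eligibility rule. Section 9.2 defines it by CT findings under the FOxTROT definition, without reference to the Appendix 2 boxes, and selection passes through MDT discussion (section 9.1).
- *Each cohort loses node-positive patients.* Section 8.1 allows recruitment to continue until 10 node-positive patients are reached, so the likely worst result is slower accrual. Any figure would rest on a share of affected tumours that the documents do not give.
- *Organ invasion through a non-peritonealised surface is also mis-staged.* Both T4 captions do require serosal penetration, but the protocol never says how TNM 5 classes that case. Appendix 3 gives only the peritoneal rule.

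**Conclusion.** The point holds as a defect in the form. Read as written, the CT T-stage boxes are not exhaustive, and they disagree with the protocol's own pT4 rule for a tumour that penetrates the serosa without organ extension or perforation. The damage falls on the secondary endpoint of standardised CT reporting and on the form that informs the evaluation phase. There may be some blurring of who counts as CT T4 for enrichment, but its direction and size cannot be established from the documents. The primary objective, the dose-selection step and both progression rules are untouched.

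The conclusion rests on two assumptions: that the captions are the criteria readers will apply, and that serosa and peritoneal surface mean the same surface in the two appendices. It needs no figure from outside the protocol.

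**What to change.** Reword the T4 part of the T-stage block in Appendix 2 so that:

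- penetration of the serosal or peritoneal surface is enough by itself for T4, in line with Appendix 3;
- adjacent-organ extension stays as its own T4 sub-item;
- bowel perforation becomes a separate yes/no item and is no longer a condition for a T4 box.

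State in section 9.2 that the enrichment criterion uses T4 in this sense, so that the three places agree.

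The cost is one reworded block on the case report form, with no extra scan. If forms have already been completed, the T item on them should be re-read against the new wording. The change is best made before the proforma is handed to the evaluation phase.

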Appendix 3: Histopathology proforma

Introduction

The guidance below is provided to assist the key role of the histopathologist in the assessment of the excised colon cancer specimens.

In the study, the local histopathologist will be involved in the following:

- i) Taking digital photographs of the whole intact fresh resection specimen including both anterior and posterior views (any clips identifying fluorescent lymph nodes should be clearly visible)
- ii) Taking digital photographs of the whole formalin-fixed resection specimen including both anterior and posterior views (any clips identifying fluorescent lymph nodes should be clearly visible)
- iii) Taking digital photographs of the serial cross-sectional slices from the resection specimen
- iv) Submitting a specimen sketch detailing the estimated position of all lymph nodes (positive and negative) according to station number (see diagram below)
- v) Submitting the final histopathology report with full histopathological staging data for review
- vi) Submitting all of the H&E stained glass slides (or copies) for central review
- vii) Submitting the formalin-fixed paraffin-embedded tissue blocks of all of the lymph nodes (and the additional two blocks of tumour and one of normal mucosa if the patient has consented)

Thank you for your efforts and for participating. The key issues are photography, consistent dissection and making the slides /blocks available for central review.

Preparation of the specimen and photography

Dissection should be undertaken using the method described here which is consistent with the

Royal College of Pathologists guidelines for reporting colorectal cancer and other colon cancer clinical trials including MRC CLASICC and NCRI FOxTROT.

The fresh specimen should be carefully examined by the local histopathologist as soon as possible after surgery to determine the plane of surgery and measure the length of the different vascular ties. If there is to be a delay before delivery of the specimen to the pathology department, it is acceptable to refrigerate the fresh specimen for up to 24 hours rather than undertake immediate fixation. The whole intact fresh specimen should have the front and back surfaces digitally photographed prior to inking of any non-peritonealised surfaces to allow central review of the quality of surgery. Any clips identifying fluorescent lymph nodes should be clearly visible. Additional pictures of any mesocolic defects or perforations would be helpful. All photographs **must** include a metric ruler scale (for calibration) and the site of the tumour and the high vascular ties should be marked (e.g. with forceps or pre-printed labels). The whole specimen should be visible in the image and mesentery should be laid out flat (not folded or over stretched). The proximal and distal aspects can also be labelled if not obvious. Photographs should be taken directly above the specimen to reduce distortion and while a white background is ideal, any other plain colour is acceptable (see figure 1).

Figure 1: Photography of the whole fresh resection specimen including anterior (left) and posterior (right) views alongside a metric scale with the tumour and high tie identified.

The photographs should not contain any direct identifiers (e.g. name or date of birth) but should be identifiable by trial number, histopathology number and patient initials.

The specimen should then be opened along the anterior aspect down to just above the tumour (but not through the tumour). The anterior surface in the area of the tumour should be preserved to allow assessment of this surface for direct and peritoneal spread. All non-peritonealised surfaces should be painted with ink e.g. India ink (figure 2). It should be remembered that the circumferential margin only applies to the surgically incised mesocolic planes (e.g. the retroperitoneal margin in right sided specimens and the upper mesorectal margin in left sided specimens) and not to the peritonealised surfaces.

Figure 2: Dissection method showing inking of the retroperitoneal margin and cross sectioning to assess tumour spread. Note the metric scale in the images.

Specimen dissection, cross-sectional slicing and photography

After the non-peritonealised surfaces have been inked, and the specimen fixed in formalin for a minimum of 2 days, it should then be described in detail and a confirmation of the quality of surgery should be undertaken (see below for further details). The formalin fixed-specimen should also be photographed if possible prior to further dissection. Again, any clips identifying fluorescent lymph nodes should be clearly visible. The specimen should then be carefully assessed for the presence of a perforation, which may be either through the tumour (tumour perforation) or through the bowel wall proximal/distal to the tumour segment (bowel

perforation). The site of the tumour and its maximum dimension should be described along with the minimum distance to the nearest longitudinal margin. A measurement should be taken on the fixed specimen between the tumour and the closest high tie vessel. The specimen should then be thinly (3-5mm) sliced transversely from 2 cm below to 2 cm above the tumour. The slices should also be photographed as a valuable demonstration of the quality of the surgery. These can be taken all together as shown in figure 2. Additional close ups of all tumour bearing slices would be helpful or alternatively all of the slices may be photographed individually. It should be clear which are the most proximal and distal slices (e.g. by using labels) and all photographs must contain a metric scale e.g. ruler (figure 2).

Not opening the specimen through the tumour segment facilitates comparison of the cross sectional slices with MRI/CT imaging. The slices should be carefully inspected and the position of the tumour recorded according to the quadrants of involvement. The distance of direct spread outside the muscularis propria and the distance from the tumour to the nearest non-peritonealised margin should be recorded along with the tumour thickness. These measurements should be made initially from the slices and confirmed histologically e.g. by using the Vernier scale. Large blocks should be taken from the area closest to the circumferential margin wherever possible and also from any area where the tumour extends to within 3 mm of the non-peritonealised margin. Other blocks should be taken to allow at least 5 blocks of tumour to confirm presence or absence of extramural venous invasion. The number of any large blocks containing tumour can be subtracted from these 5. Likewise the peritoneal surface should be sampled by a minimum of 2 blocks if the tumour impinges on it (figure 3).

All of the local lymph nodes in the specimen should be identified, mapped, embedded and examined. The high tie (apical node) should be blocked separately to allow Dukes' staging to be conducted as should any lymph nodes marked (e.g. with a clip) by the surgeons to allow comparison with the intra-operative staging. The number of lymph nodes identified in each station (see below) should be noted on a diagram for subsequent mapping. If the nodes have not been marked by the surgeons, multiple nodes from the same station may be embedded in one block to cut down on the workload.

Figure 3: Suspected peritoneal/serosal involvement by tumour.

Histological reporting

We are using both Dukes' and TNM 5 for histopathological staging in this study, not TNM 6 or 7. This is because of the poor reproducibility of the TNM 6 definitions of extramural vascular invasion and lymph nodes. Thus we will be using the 3mm rule for nodal involvement, although these will be captured separately on the CRF. This allows the study to be consistent with other trials such as the Dutch TME trial and MRC CR07 trial. Dukes' staging allows easy communication between surgeons and the clinical team whereas TNM 5 gives more prognostic information, especially with respect to early tumours and local spread, e.g. peritoneal and direct spread (figure 3).

The non-peritonealised resection margin is considered involved (i.e. an incomplete excision) if the tumour extends to within 1 mm of the inked margin. Measurement is best made by using a sheet of graph paper that is photocopied onto a sheet of acetate and cut to size. This can be provided if required and may be more easily used than the Vernier scale. This is shown in figure 4 and can also be used for measuring the EMVI to see if it is greater than 3 mm. No distinction is currently made between the various modes of non-peritonealised resection

margin involvement, e.g. direct spread, lymph node spread, vascular, etc. Although all are associated with an increased local recurrence rate, this may be lower in the case of involvement by tumour within a lymph node.

Figure 4: Rapid measurement of the distance from the tumour to the non-peritonealised resection margin by overlaying a simple grid.

Peritoneal involvement (pT4) should be diagnosed if tumour cells penetrate the peritoneal surface (figure 5).

Figure 5: Peritoneal involvement should be assessed by the method of Shepherd et al 1995 whereby tumour cells should be seen to penetrate through the serosa to lie on the surface of the specimen.

The grade of differentiation of the tumour should be defined by the predominant area of tumour and not on the area of the worst grade. Other types of differentiation, i.e. mucinous adenocarcinomas, signet ring and undifferentiated should be documented.

Grading the quality of surgery (mesocolic resection)

The quality of the mesocolic resection can be easily assessed using a combination of assessing the fresh specimen, fixed specimen and cross sectional slices. We recommend a three grade classification (table 1, figures 6/7), first used in the MRC CLASICC trial and subsequently used in NCRI FOxTROT. These systems have been demonstrated to be usable in the context of phase III clinical trials and have been shown to predict a higher risk of local recurrence in MRC CLASICC and overall survival in a large Leeds study. A second assessment of surgical planes will be made during the central review to identify inter-observer agreement. This will be done on the digital photographs.

Plane of	Short	Detailed description
dissection	description	
Mesocolic	Good quality	There should be an intact and smooth mesocolic
plane	specimen	surface with only minor irregularities. Any
		peritoneal or fascial defects must be no deeper
		than five millimetres. There should be smooth
		retroperitoneal and mesocolic resection margins
		on the cross-sectional slices
Intramesocolic plane	Moderate quality specimen	There may be moderate bulk to the mesocolon but significant irregularity of the peritoneal or fascial surface in at least one area that is deeper than five millimetres. The muscularis propria should not be visible. There may be moderate irregularity of the retroperitoneal and mesocolic
		resection margins on the cross-sectional slices
Muscularis	Poor quality	There may be little bulk to the mesocolon and
propria	specimen	there will be extensive defects that extend down

plane	to the muscularis propria. The retroperitoneal and
	mesocolic resection margins may be partially
	formed by the muscularis propria on the cross-
	sectional slices

Table 1: A detailed description of the pathological grading system used to describe the plane of dissection in colon cancer specimens.

Figure 6: Three fresh colon cancer specimens resected in the (A) mesocolic plane with an intact peritoneal window (arrow), (B) intramesocolic plane with a significant mesocolic defect (arrow), and (C) muscularis propria plane with a posterior perforation of the specimen (arrow).

Figure 7: Cross-sectional slices from three specimens resected in the (A) mesocolic plane, (B) intramesocolic plane with a significant mesocolic defect (arrow), and (C) muscularis propria plane with a defect extending down to the muscularis propria (arrow).

Mapping the lymph node stations

The specimen will be carefully dissected to map the location of all of the lymph nodes identified using the Japanese station sub-groupings (figure 8, table 2). The pathologist will mark on a specimen diagram and lymph node mapping table the number of nodes in each station and how many of these were fluorescent intra-operatively. An accurate block key will be kept so that it is clear which nodes belong to which station and whether or not they were fluorescent. The D1 nodes will be subdivided into those within 5cm of the tumour, those that lie between 5 and 10cm of the tumour and those that are more than 10cm beyond the tumour. Any non-fluorescent nodes in the same station may be embedded with more than one node in each block. Each fluorescent node will be blocked out individually. The apical node(s) will also be blocked separately to enable Dukes' staging.

As stated in TNM 5, extramural tumour deposits measuring ≥3 mm in maximum size are **Sponsor:** University of Leeds (GS11/9681)

counted as involved lymph nodes even if no residual lymph node structure can be identified. Smaller deposits are regarded as apparent discontinuous extensions of the main tumour. The number of ≥3mm tumour deposits classified as lymph nodes should be indicated in the report. Any tumour deposits measuring >3mm (and therefore counted as lymph nodes under TNM 5) should also be mapped and blocked carefully.

The local pathologist will cut a single section from each lymph node block and report the number of positive and negative nodes in each station using conventional histopathology. A copy of the diagnostic glass H&E slides, pathology report, photographs, specimen sketches and lymph node blocks will then be sent to Leeds for central review. Deeper levels and immunohistochemical testing will be used on the lymph node blocks to confirm their status and detect missed metastases, micrometastases and isolated tumour cells. A final lymph node report will be issued identifying how many lymph nodes in each station were detected, how many were involved by tumour, and how this related to the intra-operative fluorescent nodes.

Figure 8: Japanese staging subgroups - Pericolic, D1 lymph nodes (red); Intermediate D2 **Sponsor:** University of Leeds (GS11/9681) lymph nodes (blue); Main, D3, lymph nodes (yellow).

Station	All nodes	Notes	Fluorescent	Cassette	Involved
number					
201	1	5-10cm	No	A1	No
	2	5-10cm	No	A1	No
	3	5-10cm	No	A1	No
	4	<5cm	Yes	A2	Yes
	5	<5cm	No	A3	No
	6	<5cm	No	A3	No
202	1		No	A4	No
	2		No	A4	No
	3		Yes	A5	No
203	1	Apical (ileocolic)	No	A6	No
	2		No	A7	No
	3		No	A7	No
	4		No	A7	No
211	1	>10cm	No	A8	No
	2	>10cm	No	A8	No
	3	5-10cm	No	A8	No
	4	5-10cm	No	A8	No
	5	<5cm	No	A9	No
	6	<5cm, deposit >3mm	No	A9	No
	7	<5cm	No	A9	No
212	1		No	A10	No

	2		No	A10	No
	3		No	A10	No
	4		No	A11	No
	5		No	A11	No
213	1	Apical (right colic)	No	A12	No
	2		No	A13	No
TOTAL	27 nodes		2 nodes		1 node

Table 2: Example of how to map the lymph nodes for central review for a right hemicolectomy specimen including the station number, number of nodes in each station, whether the node was fluorescent, the cassette the node has been embedded in and whether or not it is involved. Note that comments have been provided to identify the apical nodes (there may be more than one apical node if the tumour lies between two vascular ties) and any nodes that are tumour deposits >3mm. Also the pericolic (D1) node are sub-classified into those >10cm from the tumour, 5-10cm from the tumour and <5cm from the tumour. The apical node(s) and any fluorescent nodes are embedded separately. All other nodes from the same station can be embedded in the same block, however, please do not embed more than four nodes in the same cassette.

